11.1 Definitions

11.1.1 Unanticipated Problems Involving Risk to Subjects or Others (UPIRTSO)

Any unanticipated problem or adverse event that meets the following three criteria:

• Serious: Serious problems or events that results in significant harm, (which may be physical, psychological, financial, social, economic, or legal) or increased risk for the subject or others (including individuals who are not research subjects). These include: (1) death; (2) life threatening adverse experience; (3) hospitalization - inpatient, new, or prolonged; (4) disability/incapacity - persistent or significant; (5) birth defect/anomaly; (6) breach of confidentiality and (7) other problems, events, or new information (i.e. publications, DSMB reports, interim findings, product labeling change) that in the opinion of the local investigator may adversely affect the rights, safety, or welfare of the subjects or others, or substantially compromise the research data, **AND**

- Unanticipated: (i.e. unexpected) problems or events are those that are not already described as potential risks in the protocol, consent document, or not part of an underlying disease. A problem or event is "unanticipated" when it was unforeseeable at the time of its occurrence. A problem or event is "unanticipated" when it occurs at an increased frequency or at an increased severity than expected, **AND**
- Related: A problem or event is "related" if it is possibly related to the research procedures.

11.1.2 Adverse Event

An untoward or undesirable experience associated with the use of a medical product (i.e. drug, device, biologic) in a patient or research subject.

11.1.3 Serious Adverse Event

Adverse events are classified as serious or non-serious. Serious problems/events can be well defined and include;

- death
- life threatening adverse experience
- hospitalization
- inpatient, new, or prolonged; disability/incapacity
- persistent or significant disability or incapacity
- birth defect/anomaly

and/or per protocol may be problems/events that in the opinion of the sponsor-investigator may have adversely affected the rights, safety, or welfare of the subjects or others, or substantially compromised the research data.

All adverse events that do not meet any of the criteria for serious, should be regarded as **non-serious adverse events**.

11.1.4 Adverse Event Reporting Period

For this study, the follow-up period is defined as up to 10 minutes after arrival to PACU or TOF ratio is > 0.9 (whichever occurs first).

11.1.5 Preexisting Condition

A preexisting condition is one that is present at the start of the study. A preexisting condition should be recorded as an adverse event if the frequency, intensity, or the character of the condition worsens during the study period.

11.1.6 Post-study Adverse Event

All unresolved adverse events should be followed by the sponsor-investigator until the events are resolved, the subject is lost to follow-up, or the adverse event is otherwise explained. At the last scheduled visit, the sponsor-investigator should instruct each subject to report, to the sponsor-investigator, any subsequent event(s) that the subject, or the subject's personal physician, believes might reasonably be related to participation in this study.

11.1.7 Hospitalization, Prolonged Hospitalization or Surgery

Any adverse event that results in hospitalization or prolonged hospitalization should be documented and reported as a serious adverse event unless specifically instructed otherwise in this protocol. Any condition responsible for surgery should be documented as an adverse event if the condition meets the criteria for an adverse event.

Neither the condition, hospitalization, prolonged hospitalization, nor surgery are reported as an adverse event in the following circumstances:

• Hospitalization or prolonged hospitalization for therapy of the target disease of the study, unless it is a worsening or increase in frequency of hospital admissions as judged by the clinical investigator.

11.2 Recording of Adverse Events

At each contact with the subject, the study team must seek information on adverse events by specific questioning and, as appropriate, by examination. Information on all adverse events should be recorded immediately in the source document, and also in the appropriate adverse event section of the electronic case report form (CRF). All clearly related signs, symptoms, and abnormal diagnostic, laboratory or procedure results should recorded in the source document.

All adverse events occurring during the study period must be recorded. The clinical course of each event should be followed until resolution, stabilization, or until it has been ultimately determined that the study treatment or participation is not the probable cause. Serious adverse events that are still ongoing at the end of the study period must be followed up, to determine the final outcome. Any serious adverse event that occurs during the Adverse Event Reporting Period and is considered to be at least possibly related to the study treatment or study participation should be recorded and reported immediately.

11.3 Reporting of Serious Adverse Events and Unanticipated Problems

When an adverse event has been identified, the study team will take appropriated action necessary to protect the study participant and then complete the Study Adverse Event Worksheet

and log. The sponsor-investigator will evaluate the event and determine the necessary follow-up and reporting required.

11.3.1 Sponsor-Investigator reporting: notifying the Mayo IRB

The sponsor-investigator will report to the Mayo IRB any UPIRTSOs and Non-UPIRTSOs according to the Mayo IRB Policy and Procedures. Each participating site will report SAEs to their respective IRB or Ethics Committee with copy of submission and review provided to the leading site. Should there be any SAEs at any of the participating sites; the study team at that site will notify the primary site (Mayo Clinic in Florida) within 24 hours of learning of the event.

Any serious adverse event (SAE) which the Principal Investigator has determined to be a UPIRTSO will be reported to the Mayo IRB as soon as possible but no later than 5 working days after the investigator first learns of the problem/event.

The following information will be collected on the adverse event worksheet (and entered in the research database):

- Study ID
- Disease
- The date the adverse event occurred
- Description of the adverse event
- Relationship of the adverse event to the research device*
- Determination if the adverse event was expected
- The severity of the adverse event (severity scale described below**)
- If any intervention was necessary
- Resolution (was the incident resolved spontaneously, or after discontinuing treatment)
- Date of Resolution

The sponsor-investigator will review all adverse event reports to determine if specific reports need to be made to the IRB. The sponsor-investigator will sign and date the adverse event report when it is reviewed. For this protocol, only directly related SAEs/UPIRTSOs will be reported to the IRB.

* Relationship Index

The relationship of an AE to the Investigational Device is a clinical decision by the sponsor-investigator (PI) based on all available information at the time of the completion of the eCRF and is graded as follows:

1. Not related: a reaction for which sufficient information exists to indicate that the etiology is unrelated to the use and proper application of study device.

2. Unlikely: a clinical event, including laboratory test abnormality, with a temporal relationship to use of the study device which makes a causal relationship improbable and in which use of other devices, chemicals, or underlying disease provide plausible explanations.

- 3. Possible: a clinical event, including laboratory test abnormality, with a reasonable time sequence to use of the study device but which could also be explained by concurrent disease or use of other devices or chemicals.
- 4. Probable: a clinical event including laboratory test abnormality, with a reasonable time sequence to use of the study device, unlikely to be attributed to concurrent disease or use of other devices or chemicals.
- 5. Definite: a reaction that follows a reasonable temporal sequence from the use of the study device.

** Severity Scale

The maximum intensity of an AE during a day should be graded according to the definitions below and recorded in details as indicated on the CRF. If the intensity of an AE changes over a number of days, then separate entries should be made having distinct onset dates.

- 1. Mild: AEs are usually transient, requiring no special treatment, and do not interfere with patient's daily activities.
- 2. Moderate: AEs typically introduce a low level of inconvenience or concern to the patient and may interfere with daily activities, but are usually ameliorated by simple therapeutic measures.
- 3. Severe: AEs interrupt a patient's usual daily activity and traditionally require systemic drug therapy or other treatment.

11.4 Medical Monitoring

It is the responsibility of the Principal Investigator to oversee the safety of the study at his/her site. This safety monitoring will include careful assessment and appropriate reporting of adverse events as noted above, as well as the construction and implementation of a site data and safety-monitoring plan (see section 10 "Study Monitoring, Auditing, and Inspecting"). Medical monitoring will include a regular assessment of the number and type of serious adverse events.

12 Data Handling and Record Keeping

12.1 Confidentiality

Information about study subjects will be kept confidential and managed according to the requirements of the Health Insurance Portability and Accountability Act of 1996 (HIPAA). Those regulations require a signed subject authorization informing the subject of the following:

• What protected health information (PHI) will be collected from subjects in this study

- Who will have access to that information and why
- Who will use or disclose that information
- The rights of a research subject to revoke their authorization for use of their PHI.

In the event that a subject revokes authorization to collect or use PHI, the investigator, by regulation, retains the ability to use all information collected prior to the revocation of subject authorization. For subjects that have revoked authorization to collect or use PHI, attempts should be made to obtain permission to collect at least vital status (long term survival status that the subject is alive) at the end of their scheduled study period.

12.2 Source Documents

Source data is all information, original records of clinical findings, observations, or other activities in a clinical trial necessary for the reconstruction and evaluation of the trial. Source data are contained in source documents. Examples of these original documents and data records include: hospital records and any forms completed specifically for this study.

12.3 Case Report Forms

All data necessary for this study will be obtained from EHR or at the time devices are being used and recorded on the electronic Case Report Forms (CRFs) created in REDCap. All missing data will be explained.

12.4 Data Management

Study data to be collected and managed using EHR and study-generated source documents and transcribed into electronic CRFs in REDCap, electronic data capture software, hosted by CTSA at Mayo Clinic. REDCap (Research Electronic Data Capture) is a secure, web-based application designed to support data capture for research studies, providing 1) an intuitive interface for validated data entry; 2) audit trails for tracking data manipulation and export procedures; 3) automated export procedures for seamless data downloads to common statistical packages; and 4) procedures for importing data from external sources.

12.5 Data Processing

All study date will be stored and analyzed at Mayo Clinic in Florida using the REDCap electronic data capture tool.

12.6 Data Security and Confidentiality

All source documents including clinical findings, observations or other activities will be stored in a REDCap database that will be designed by an Investigator. Access to the REDCap database

will be limited to the Principal Investigator, Investigators, Study Team members, and Statistician.

12.7 Data Quality Assurance

Once the study is completed the Principal Investigator will randomly select 3 participants and compare the data documented in the EHR with what is entered into the REDCap database. If there is any discrepancy, the Principal Investigator and/or Investigators will cross-reference all 35 patients to ensure accuracy.

12.8 Data Clarification Process

For any data query the Principal Investigator and Investigators will meet to clarify the data queried and make corrections based on consensus.

12.9 Records Retention

The sponsor-investigator will maintain records and essential documents related to the conduct of the study. These will include subject case histories and regulatory documents. Principal Investigator will maintain regulatory and essential study documents to ensure compliance with local and federal policies/guidelines.

The sponsor-investigator will retain the specified records and reports:

 As outlined in the Mayo Clinic Research Policy Manual –"Retention of and Access to Research Data Policy"

13 Study Monitoring, Auditing, and Inspecting

13.1 Study Monitoring Plan

The investigator will allocate adequate time for such monitoring activities. The Investigator will also ensure that the compliance or quality assurance reviewer is given access to all the study-related documents.

13.2 Auditing and Inspecting

The investigator will permit study-related monitoring, audits, and inspections by the IRB, the sponsor, and government regulatory agencies, of all study related documents (e.g. source documents, regulatory documents, data collection instruments, study data etc.).

Participation as an investigator in this study implies acceptance of potential inspection by government regulatory authorities and applicable compliance offices.

14 Ethical Considerations

This study is to be conducted according to United States and International government regulations and Institutional research policies and procedures.

This protocol and any amendments will be submitted to a properly constituted local Institutional Review Board (IRB), in agreement with local legal prescriptions, for formal approval of the study. The decision of the IRB concerning the conduct of the study will be made in writing to the sponsor-investigator before commencement of this study.

All subjects for this study will be provided a consent form describing this study and providing sufficient information for subjects to make an informed decision about their participation in this study. This consent form will be submitted with the protocol for review and approval by the IRB for the study. The formal consent of a subject, using the Approved IRB consent form, must be obtained before that subject undergoes any study procedure. The consent form must be signed by the subject and the individual obtaining the informed consent.

15 Study Finances

15.1 Funding Source

This investigator initiated study is not funded. Study coordinator's time is supported by the Department of Anesthesiology and funding for statistical analysis will be provided from the Principal Investigator's research fund.

15.2 Conflict of Interest

Any study team member who has a conflict of interest with this study (patent ownership, royalties, or financial gain greater than the minimum allowable by their institution, etc.) must have the conflict reviewed by a properly constituted Conflict of Interest Committee with a Committee-sanctioned conflict management plan that has been reviewed and approved by the study sponsor-investigator prior to participation in this study.

No financial conflicts of interested are anticipated or have been identified for this study.

18.1 Schedule of Events

	Schedule of Events						
Study Activity	Visit 1	Visit 2					
Tetragraph		X					
TOFScan		X					
Informed consent	X						
Review of Medical Record	X						
Adverse event		X					

18.2 Intraoperative Data

•		Date of Surgery (dd / mm / yyyy):		Examiner's Initials:		
Wrist circumference (right):		Wrist circumference (left):		Dominant side: L / R		
Ankle circumference (right):		Ankle circumference (left):				
Age (yrs):	Weight	(kg):		Height (cm):		BMI:
Muscle relaxant name	:					
Muscle relaxant total dose (mg):						
Time of first muscle re	elaxant	dose (mm :	: hh):		:	am / pm

Reversal agent name:					
Reversal agent dose (mg)	:				
Time of reversal agent administration (mm : hh):				:	am / pm
Time of extubation:		:		am / pm	

TetraGraph (TG) / TOFScan

	Time	TetraGraph (TG) Arm L/R	TOFScan Arm L / R	TOFR # 3 (if needed)
Calibrated baseline TOFR and supramax current				
TOFC=0 (post initial dose of NMBA)				
Time Interval (first recheck)				
Time Interval (second recheck)				
Time Interval				
Time Interval				
Time Interval				

Time Interval		
Time Interval		

Time Interval		
pre-SGX		
+60sec after SGX		
+120 sec after SGX		
+180 sec after SGX		
+260 sec after SGX		
Extubation		
Time to recovery following SGX (TOFR ≥0.9)		
T0 (on arrival to PACU)		
T5 (5 min after PACU arrival)		
T10 (10 min after PACU arrival)		

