Overall Study Duration	12 months
Subject Participation Duration	2 – 5 hours
Single or Multi-Site	Multi site
Objectives	The primary aim of this study is to compare the ease of use and repeatability of AMG vs. EMG neuromuscular responses in surgical settings in which the patients' arm movement is restricted (placed under surgical drapes) in laparoscopic or robotic procedures.
Number of Subjects	105
Diagnosis and Main Inclusion Criteria	Patients undergoing elective robotic or laparoscopic surgery and requiring administration of neuromuscular blocking agents intraoperatively
Study Device	TetraGraph and TOFScan
Duration of Administration	Single stimulation of ulnar nerve repeated at specific intervals as outlined in the Study Procedures (Section 9.2)

4 Introduction

This document is a protocol for a human research study. This study will be carried out in accordance with the applicable United States government regulations and Mayo Clinic research policies and procedures.

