
Many clinicians default to the antiquated practice of subjective monitoring (18, 19), which refers to visual or tactile evaluation of the train-of-four (TOF) in response to neurostimulation provided by peripheral nerve stimulation. However, subjective evaluation may provide inaccurate information and assessment of full recovery compared to objective evaluation (20, 21). A consensus statement by the international panel of experts in neuromuscular blockade issued in 2018 state that subjective evaluation is not predictive of adequate neuromuscular recovery, and is not sensitive to the presence of residual weakness. They state that their use should be abandoned

in favor of objective monitoring, because after the TOFR recovers to >0.40, anesthesia providers can no longer detect the presence of fade by subjective evaluation and they may assume a complete recovery from neuromuscular blockade, despite the presence of minimal levels of NMB(16). It is worth highlighting that after tracheal extubation, even minimal degrees of residual block is associated with impaired function of respiratory and pharyngeal muscles, upper airway obstruction (22),hypoxemia (23), and awareness during anesthesia (24)

Utilizing recommendations from the Good Clinical Practice (GCP) Guidelines for monitoring of neuromuscular function (25), we will compare acceleromyographic and electromyographic responses to train-of-four stimulation of the ulnar nerve in surgical settings where the arm movement is restricted by the surgical drapes (such as laparoscopic and robotic surgery). The time points of interest will include the onset of blockade following neuromuscular relaxant administration, maintenance of block, and reversal of blockade with sugammadex or neostigmine until adequate recovery (train-of-four ratio >0.9). The reliability of the two monitors will be evaluated post hoc by comparing the repeatability of responses, and the usability of the two monitors will be evaluated by the healthcare providers using the System Usability Scale (SUS) Plus scale, a simple, 10-item Likert scale with 5 response options for the evaluators (https://www.usabilitest.com/system-usability-scale).

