4.3 Risks and Benefits

- The benefits of using neuromuscular blockade monitoring devices:
 Early detection of optimal time for tracheal extubation; optimal management of intraoperative depth of neuromuscular block to facilitate surgical procedures; determination of appropriate time and dose of sugammadex reversal; and detection of residual neuromuscular blockade. This is currently the standard of care practice at Mayo Clinic.
- The risks of using neuromuscular blockade monitoring devices: Slight discomfort when electrical stimulation is administered in awake volunteers; however, our patients will be anesthetized, rendering this risk as extremely minor.

5 Study Objectives

Primary Objective

Compare the objective EMG-derived data using TetraGraph (TOFR, TOFC, PTC) with those obtained from the AMG-based TOFScan monitor and assess the reliability and usability of the two objective monitors.

Secondary Objective

Determine the incidence of failure to calibrate and monitor neuromuscular responses using the two monitors.

6 Study Design

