9.2 Visit 2 (Randomization and Treatment – day of surgery)

- Elective surgical procedure as in which intraoperative access to the arms is restricted because of surgical draping.
- Anesthetic management will be standardized to utilize rocuronium, sevoflurane, and sugammadex or neostigmine at the discretion of the attending anesthesiologist
- Prior to induction of anesthesia, the Tetragraph electrodes will be placed over the ulnar nerve and the thumb to measure the response of adductor pollis nerve. Randomization will be performed utilizing REDCap and involves the use of dominant vs non-dominant arm.

• Following induction of anesthesia but prior to NMBA administration, baseline values will be recorded from both monitors after calibration.

- Anesthesia providers will have access to the TetraGraph and TOFScan values during the
 entire procedure, and will make clinical decisions as per usual clinical routine at Mayo
 Clinic.
- After NMBA administration, sets of measurements will be taken with the two monitors at regular intervals (every 12 sec, 20 sec, 1 min, 15 min, etc.) as required per usual clinical routine and determined by the anesthesia attending.
- Near the conclusion of the operation but prior to the reversal of neuromuscular block, another set of measurements will be taken, with the two monitors, as per usual clinical routine, in order to determine the appropriate reversal drug dosage.
- After sugammadex or neostigmine administration, measurements will be taken every 20 seconds until return of neuromuscular function is documented.
- Following documentation of adequate neuromuscular function (TOF ratio is >0.9,) the devices will be removed and the patient will proceed along the standard recovery pathway.

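### Repeatability is in the stated primary aim, but the form schedules no repeat reading at an unchanged block and the analysis section names no repeatability statistic

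*Combined protocol and SAP*

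**What the plan says.** The Study Summary (section 3) gives the primary aim as to "compare the ease of use and repeatability of AMG vs. EMG neuromuscular responses" where arm movement is restricted. 4.2 Background adds: "The reliability of the two monitors will be evaluated post hoc by comparing the repeatability of responses". The primary objective in section 5 is partly to "assess the reliability and usability of the two objective monitors". The endpoints are narrower: 6.4 names usability on the SUS Plus scale, and 6.5 measures reliability by how often each monitor fails to calibrate or measure. 10.2.1 plans Bland-Altman agreement between the monitors and the SUS comparison. No section defines a within-monitor repeatability statistic.

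On data capture, 6.6 sends the study data points to the CRF. Table 18.2 gives each row one TetraGraph cell, one TOFScan cell and an optional TOFR # 3 column that is not tied to either monitor. There is one baseline row, "Calibrated baseline TOFR and supramax current", then a row for loss of all twitches, eight open Time Interval rows and a pre-reversal row. The timed rows after reversal are at +60, +120 and +180 s, and the last is "260 sec after SGX". Extubation, time to recovery and three PACU rows follow.

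9.2 is denser than the form: "After sugammadex or neostigmine administration, measurements will be taken every 20 seconds until return of neuromuscular function is documented". Once TOF ratio is above 0.9, the "devices will be removed and the patient will proceed along the standard recovery pathway". 8.1 describes an SD-card recording and download for TetraGraph. For TOFScan it says that the device can measure and record, and describes no download.

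**The concern.** Repeatability is the scatter of one monitor's readings while the quantity measured stays the same. Estimating it needs at least two readings per monitor at an unchanged block, and the form requires none. The rows after reversal are successive readings, but TOF ratio is rising between them, so their differences mix measurement error with true recovery. The PACU rows might have served as near-stable repeats, but 9.2 takes the devices off first in any patient who recovers in the operating room.

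At stake is the repeatability half of the stated aim. The investigators would have to choose an estimator after seeing the data. They might also take the two monitors' readings from sources with different spacing, which alone can make equal monitors look different.

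**Working it through.** The plan gives no repeatability figure to reproduce. Its only sample-size figure (10.1: 23 patients, SD 0.07) concerns a mean difference in TOF ratio and is not touched by this point.

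**Inputs from the documents.** 105 patients (10.1); one baseline cell per monitor and post-reversal gaps of 60, 60 and 80 s (Table 18.2); 20 s readings after reversal (9.2); SD 0.07 (10.1).

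**Assumptions.** The true repeatability SD is s = 0.05, about 0.07/√2 if 0.07 is the SD of differences between devices. That value came from volunteers and another AMG device. TOF ratio rises in a straight line from 0 to 0.9 in R = 180, 260 or 600 s.

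**Step 1: scheduled repeats at a stable block.** At baseline, degrees of freedom per monitor = 105 × (1 − 1) = 0.

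**Step 2: what successive recovery rows would give.** If the true change between readings is δ = 0.9 × gap/R, the SD from successive differences is √(s² + mean(δ²)/2). Only rows at or before R are used.

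| | R = 180 s | R = 260 s | R = 600 s |
|---|---|---|---|
| δ, form rows | 0.30, 0.30 | 0.208, 0.208, 0.277 | 0.09, 0.09, 0.12 |
| SD, form rows | 0.218 | 0.172 | 0.087 |
| δ, 20 s readings | 0.10 | 0.069 | 0.03 |
| SD, 20 s readings | 0.087 | 0.070 | 0.054 |
| Ratio, equal monitors, form rows vs 20 s log | 2.52 | 2.46 | 1.60 |
| True SDs 0.10 vs 0.05, form rows for both | 1.08 | 1.12 | 1.41 |
| True SDs 0.10 vs 0.05, 20 s readings for both | 1.41 | 1.59 | 1.88 |

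Repeats at a stable block would show the true ratio of 2.00.

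**Step 3: can the trend be removed afterwards?** A line fitted per patient to the four rows leaves 2 df and returns 0.05 if recovery really is straight. Suppose instead TOF ratio = 1 − exp(−t/100). The rows then read 0.451, 0.699, 0.835 and 0.926, and the residual sum of squares about the line is 0.0104. The SD becomes √(0.0025 + 0.0104/2) = 0.088. Other curved shapes gave up to 0.157.

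A Grubbs-type estimator (half of variance minus covariance of the row-to-row changes) needs no recovery shape, but it needs both arms to share one true value. Let one monitor read 10% higher and let M be the mean squared true change. The two estimates become s² − 0.05M and s² + 0.055M. In the exponential example, M = (0.248² + 0.136² + 0.091²)/3 = 0.029, giving 0.0010 and 0.0041 for a true variance of 0.0025.

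**Step 4: what scheduled repeats would buy.** Three readings at one stable point give 105 × 2 = 210 df per monitor if every patient has a TOF ratio. The 95% chi-square interval for the SD is 0.91 to 1.11 times the estimate. An SD ratio of about 1.25 is detectable with 90% power at two-sided 0.05, treating the monitors as independent.

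**The case against.** A reader might infer that TOFScan repeatability can never be separated from recovery, or that the whole form holds zero degrees of freedom for it. The documents do not support that. 9.2 lets the attending choose intervals as short as 12 or 20 s during maintenance, and eight Time Interval rows could hold such near-repeats. The TOFR # 3 column could hold another reading. 8.1 says that TOFScan records, and 12.3 also names the EHR as a source, so dense TOFScan data are undescribed rather than excluded. What stands against this is that none of it is required, and during block a reading may be only a count. The zero in Step 1 is therefore a count of scheduled stable-state repeats at baseline.

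A reader might also take the 2.5-fold ratio as a forecast of bias against TOFScan. It is not: no section plans to set the TetraGraph log against TOFScan form rows with trend left in. It illustrates what mixing sources would do.

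The best technical defence is that detrending or a Grubbs-type estimator could rescue the form's data. Each works when its assumption holds. Step 3 shows that neither is robust, and 10.2.1 specifies neither.

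Finally, no formal endpoint depends on repeatability, since 6.4 and 6.5 name SUS and failure frequency. That is right and limits the weight of the point. It does not remove the aim in the Study Summary or the statement in 4.2.

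**Conclusion.** The point holds in a limited form. The plan promises a comparison of repeatability, but its form requires no same-state repeat on either monitor, its data description gives a download for one monitor only, and its analysis section covers agreement rather than repeatability. Without an assumption about recovery shape, or about the two arms sharing one true TOF ratio, repeatability is not estimable from the form as written.

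Under the assumed recovery times and SD, untrended form rows would inflate an SD of 0.05 to between 0.09 and 0.22 and shrink a true two-fold difference to between 1.08 and 1.41. These sizes rest on assumed inputs. The scheduling gap itself does not.

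Usability, failure frequency, sample size and the validity of the Bland-Altman pairs are unaffected. This should be changed, but it does not threaten the primary endpoint.

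**What to change.** In 9.2 and Table 18.2, record three consecutive readings about 20 s apart on both monitors at two points: (a) calibrated baseline, before the blocking agent; and (b) with the arms draped, just before reversal, entering TOFC where no TOF ratio exists.

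If a post-recovery set is wanted, start it at a fixed time after TOF ratio above 0.9 is confirmed, leave out the reading that triggered it, and keep the devices on until it is done. Starting at the first reading above 0.9 would select high values. If recovery were still continuing at the assumed rate, a triplet's SD would be √(s² + δ²) = 0.112, 0.085 or 0.058 for a true 0.05, using the 20 s δ values above.

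In 10.2.1, define repeatability as the within-patient SD of these readings for each monitor, compared between monitors, with the same data source and sampling interval for both.

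The cost is about 40 s at each point, eight more cells per patient (2 points × 2 monitors × 3 readings = 12, less the 4 already there) and two sentences in the SAP. No device export is needed. The limits are that baseline may precede draping and that pre-reversal readings may be counts only, so both points are needed. If the investigators do not want repeatability, the alternative is to remove it from the Study Summary and 4.2.
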